#### Total Activity Score of the BPDAI

**Total activity** score is defined as sum over the three activities sub-scores defined above. Higher scores indicate greater disease activity.

### BPDAI Damage / Pigmentation Total Score

BPDAI Damage / Pigmentation Total Score, ranging from 0 to 12, where higher scores indicate greater disease activity.

Note that the Damage/Pigmentation score generally rises over shorter time periods (months) because it represents post-inflammatory hyperpigmentation that can take over one year to resolve.

Damage scores that were not filled should be replaced by zero.

### Total BPDAI Score

**Total BPDAI** score is defined as sum of the Total Activity scores and BPDAI Damage / Pigmentation Score. Higher scores indicate greater disease activity.

• Change in **Total Activity Score** of BPDAI from Baseline to all subsequent visits

Change in Total Activity Score =

(Baseline Total Activity BPDAI - Visit *t* Total Activity BPDAI)

• Change in Total BPDAI Score from Baseline to all subsequent visits

Change in Total BPDAI Score = (Baseline Total BPDAI - Visit t Total BPDAI)

Note: larger positive difference indicates greater improvement.

 Percent change in Total Activity Score of BPDAI from Baseline to all subsequent visits

Percent Change in Total Score = 100\*(Baseline Total Activity BPDAI – Visit t Total Activity BPDAI) / Baseline Total Activity BPDAI

Percent change in Total BPDAI Score from Baseline to all subsequent visits
 Percent Change in Total BPDAI Score = 100\*(Baseline Total BPDAI – Visit t Total BPDAI) / Baseline Total BPDAI

Note: larger positive difference indicates greater improvement.

In addition, percent change in Total Activity score of BDPAI will be further divided into 4 categories:

- 1. # subjects with >= 90% reduction in BPDAI total activity score
- 2. # subjects with >=75% reduction in BPDAI total activity score
- 3. # subjects with >=70% reduction in BPDAI total activity score
- 4. # subjects with >= 50% reduction in BPDAI total activity score

### **Prednisone Dose**

All prednisone doses are summarized in either the Concomitant Medications form or the Corticosteroid Therapy Form depending on the protocol version used. Note that modification of prednisone doses at any time during the study was acceptable.

Therefore, both the mean dose throughout the trial and the cumulative dose will be of interest.

The following prednisone dose summaries will be provided:

- 1. For each patient, divide the relevant form records into the periods which are consistent with the study periods:
  - a. Prednisone dose at Visit 2 will be based on all records done between the Visit 2 (including) and Visit 3 (not including). A single (long) record could be split into several records to fit the trial periods. For example, if a record starts before Visit 2 and ends before Visit 3, only the relative part from Visit 2 date onwards will be related to Visit 2.
  - b. Similarly, all other trial visits will be defined, up to Visit 8.
- 2. For each patient and each trial period, calculate the total prednisone dose (mg) taken during this period. Frequency and the length of exposure should be considered in this calculation. (For example, Dose\*Frequency\*Number of Days)

- 3. The mean prednisone dose (mg/day) for each period will be calculated as the total dose in the previous step divided by the period duration (days).
- 4. The cumulative prednisone dose (mg) for each period will be calculated as the sum of the total prednisone dose (mg) over all preceding periods, starting at Visit 2.
- 5. Calculations similar to those described in steps (3) and (4) will be repeated, but with dose adjusted for a patient's weight. The mean weight adjusted prednisone dose (mg/kg/day) for each period will be calculated as the total dose in step (2) divided by the period duration (days) and divided by the subject's weight (kg) obtained at this visit (or the most recent available). The cumulative weight adjusted prednisone dose (mg/kg) for each period will be calculated as the cumulative sum over weight adjusted doses over all preceding visits.
- Reduction (measured continuously) in prednisone mean dose (mg/day) from Visit 2
   (Day 0) to each subsequent visit
- Dichotomous reduction in prednisone mean dose (mg/day) will be defined as
  - O Success "1", if the dose at Visit 8 (Day 84) does not exceed 10 mg/day
  - o Failure "0", otherwise

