6.8.2 Rescue Therapy

If necessary, rescue therapy is permitted at any point during the study at the discretion of the investigator. The patient can continue in the study as long as the rescue therapy is clearly documented.

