#### Prednisone dose

- Descriptive statistics of prednisone doses (mean dose, weight adjusted mean dose, cumulative dose and weight adjusted cumulative dose) will be presented by visit.
- Descriptive statistics of reduction in mean dose and weight adjusted mean dose will be presented by visit.
- Frequency distribution of dichotomous reduction in mean dose will be presented by visit.
- Mean plots for mean dose (mg/day), weight adjusted mean dose (mg/kg/day), cumulative dose (mg) and weight adjusted cumulative dose (mg/kg).

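### The prednisone reference labelled Visit 2 (Day 0) in SAP 7.2.1 is an on-treatment mean from Visit 2 to Visit 3, so a dose change in that window shifts every reported reduction

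*SAP*

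**What the plan says.** SAP 7.2.1 (Prednisone Dose) divides each patient's steroid records into periods that run from one visit to the next. Step 1a sets the first: "Prednisone dose at Visit 2 will be based on all records done between the Visit 2 (including) and Visit 3 (not including". Its example of a record that straddles Visit 2 discards the earlier part: "only the relative part from Visit 2 date onwards will be related to Visit 2". The later periods follow the same pattern: "Similarly, all other trial visits will be defined, up to Visit 8". Step 3 gives the averaging rule: "The mean prednisone dose (mg/day) for each period will be calculated as the total dose in the previous step divided by the period duration (days".

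The endpoint built on these means is "Reduction (measured continuously) in prednisone mean dose (mg/day) from Visit 2" (Day 0) to each subsequent visit. SAP 9.4.1 adds the weight-adjusted version: "Descriptive statistics of reduction in mean dose and weight adjusted mean dose will be presented by visit".

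The dose can move inside the first window. The SAP says so: "Note that modification of prednisone doses at any time during the study was acceptable". Under Protocol 6.8.2, "rescue therapy is permitted at any point during the study at the discretion of the investigator". Protocol 3.0 and 6.8.1 recommend the Table 1 taper for the rest of the study: 5 mg a week above 10 mg/day and 2.5 mg a week from 10 mg/day down.

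SAP 6.2.2, by contrast, defines baseline as the last measurement before treatment starts, and the BPDAI change in 7.2.1 is taken from baseline.

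**The concern.** The label names a day, but the number is a two-week on-treatment average. A reader of the study report would take a reduction from Visit 2 (Day 0) to mean a reduction from the dose at the first infusion. Under the SAP rule, a taper step in the first two weeks lowers the reference and shrinks the later reductions. A dose increase in the same two weeks raises the reference, and its later reversal is counted as reduction.

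The second effect matters more for interpretation. SAP 1.1 makes lower steroid doses the evidence of efficacy and says the results will inform decisions on further development. With no control arm and at most 15 patients, a few early increases can move the mean reduction, and nothing in the reduction figure itself would show it.

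**Working it through.** The plan gives no worked value for this endpoint, so there is no figure to reproduce. I applied SAP steps 1 to 3 to daily dose paths.

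**Inputs from the documents:** visits at Days 0, 14, 28, 42 and 56; the Table 1 steps; 30 mg/day on Day 0 (Protocol 3.0, for newly diagnosed patients who had been on 30 to 40 mg/day).

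**Assumptions:** the day of the first taper step, and the two paths with an increase. The documents give neither.

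**Formulas:** M2 = mean daily dose over Days 0 to 13. Mt = mean daily dose from Visit t up to the next visit. SAP reduction = M2 − Mt. Reduction from the Day 0 dose B = B − Mt. The two differ by B − M2 at every visit.

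**Path 1: 30 mg/day, first step on Day 7.** M2 = (7×30 + 7×25)/14 = 27.5, so B − M2 = 2.5.

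| Visit | Mt | SAP rule | Day 0 dose minus Mt | Day 0 dose minus dose on visit day |
|---|---|---|---|---|
| 3 | (20+15)/2 = 17.5 | 10.0 | 12.5 | 30−20 = 10 |
| 4 | (10+7.5)/2 = 8.75 | 18.75 | 21.25 | 30−10 = 20 |
| 5 | (5+2.5)/2 = 3.75 | 23.75 | 26.25 | 30−5 = 25 |
| 6 | 0 | 27.5 | 30.0 | 30−0 = 30 |

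With the ±2-day window, Visit 3 may fall on Day 12 or Day 16. M2 is then (7×30 + 5×25)/12 = 27.9 or (7×30 + 7×25 + 2×20)/16 = 26.6, a shift of 2.1 or 3.4 mg/day.

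**Path 2: 20 mg/day, 40 mg/day on Days 3 to 13, then 20 again.** M2 = (3×20 + 11×40)/14 = 35.7. From Visit 3 on, Mt = 20. The SAP reduction is 35.7 − 20 = 15.7 mg/day. From the Day 0 dose it is 20 − 20 = 0. If 15 patients contribute, one such patient adds 15.7/15 = 1.05 mg/day to the mean reduction.

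**Path 3: 20 mg/day, 40 mg/day from Day 7, 5 mg weekly steps from Day 14.** M2 = (7×20 + 7×40)/14 = 30. At Visit 4, Mt = (25+20)/2 = 22.5. The SAP reports a reduction of 7.5 mg/day while the period mean is 2.5 mg/day above the Day 0 dose.

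**Stable dose:** M2 = B, so there is no shift.

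**Other summaries:** the Visit 8 success criterion (at most 10 mg/day) and the cumulative dose do not use M2 as a reference. The weight-adjusted reduction does, in its weight-adjusted form.

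**The case against.** The strongest reply has four parts.

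- **Like with like.** The SAP compares one period mean with another. Putting the Day 0 dose against forward period means introduces the opposite error. In Path 1 the SAP rule agrees with the dose-on-the-day difference at Visit 3 (10), while the Day 0 dose minus the period mean gives 12.5. At Visits 4 and 5 the two errors are equal and opposite (1.25 each way). The SAP rule is clearly worse only from Visit 6. This stands, and the fix has to allow for it.
- **A strictly pre-infusion dose can be zero.** The protocol prefers newly diagnosed patients who have not been treated before, and Protocol 1.3 describes initial prednisone as added to bertilimumab. For a patient who starts prednisone with the first infusion, a pre-infusion reference allows no reduction at all. The listings in SAP 9.3.2 carry dates but no times, so a Day 0 record cannot be ordered against the infusion. This also stands.
- **The data stay visible.** The averaging rule is stated openly. Period means and cumulative doses are tabulated and plotted by visit, and dated steroid records are listed by subject. This lowers the severity, but the reduction table still carries a Day 0 label that its reference does not meet.
- **The stakes are limited.** The study is descriptive and safety is the primary objective. The protocol's own steroid endpoint is the proportion at 10 mg/day or less, and the continuous reduction appears only in the SAP. This too stands as a limit on severity.

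SAP 6.2.2 gives its baseline definition next to the BPDAI, and the prednisone endpoint does not use the word baseline. The mismatch is thus with the SAP's general convention and with the endpoint's own Day 0 label.

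**Conclusion.** The point holds in a limited form. The reference for the continuous prednisone reduction, and for its weight-adjusted version, is an on-treatment mean under a Day 0 label. Relative to the Day 0 dose, it understates reductions by 2.5 mg/day for a 30 mg/day patient whose first step is on Day 7. It reports 15.7 mg/day of reduction in the assumed rise-and-return case, where the net change is zero. These sizes rest on the assumed dose paths. The SAP gives no end for the Visit 8 period, so that visit is left out of the table.

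A reader might infer more than the documents support:

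- **That an early increase is treatment failure.** Protocol 1.3 expects steroids to act while the slower biologic takes effect, so steroid need in the first two weeks is not in itself failure of the drug.
- **That every later reduction is understated.** That depends on the comparison. Against the dose on the visit day, the SAP rule is exact at Visit 3 in Path 1.
- **That the shortfall reaches 7.5 mg/day.** From 30 mg/day this needs a first step on Day 0, giving (25+20)/2 = 22.5. That sits badly with the requirement in Protocol 3.0 that patients coming from 30 to 40 mg/day be on 30 mg/day at the first administration.
- **That the inflation can be far larger through very high early doses.** For newly diagnosed patients, Protocol 6.8.3 lists more than 40 mg/day among prohibited treatments during the study, so a 60 mg/day example would be a poor guide for them.
- **That the overall result favours the drug.** The taper is only recommended and the number of early increases is not given, so the net direction is unknown. Tapering in the window works against the drug.

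**What to change.** In SAP 7.2.1:

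1. Define the reference as the daily prednisone-equivalent dose in effect on the Visit 2 (Day 0) date, before any later change.
2. State the rule for patients who start prednisone on Day 0: use the Day 0 starting dose, flag these patients, and list their prior dose of 0.
3. Compute the unadjusted and weight-adjusted reductions from this reference.
4. Keep the present Visit 2 value, but report it as the Visit 2 to Visit 3 mean, the first on-treatment period, so that an early increase appears as an increase.
5. Show the reduction in dose on the visit day next to the period means, so that a point dose is compared with a point dose.

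The cost is SAP wording and some extra derivation from dated records that the CRF already holds. No patient procedure changes. Reported reductions will become smaller for patients whose dose rose early and, against the same period means, larger for those who tapered in the first two weeks.

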The following assessments will be performed at the follow-up clinic visits except for Visit 9 (Day 118): physical examination (including weight), BPDAI including Pruritus VAS, physician's assessment of lesion healing, completion of ABQOL questionnaire, photography, vital signs, AE and concomitant medication recording and serum collection for BP180 and BP230 autoantibody titres, PK, blood sample collection for measurement of serum eotaxin-1 and anti-bertilimumab antibodies. Skin punch biopsy for H&E staining and eosinophil count in tissue will be conducted (Visit 5 only). Urine pregnancy test (Visit 5 and Visit 8) for females of childbearing potential only), PBMC biomarker blood sampling (Visit 5 only) and safety laboratory evaluations (hematology, biochemistry) will be performed (Visits 5 and 8 only). ECG will be performed at Visit 8 (Day 84). The only assessments that will be performed on Visit 9 (Day 118) are collection of concomitant medication and adverse event information, and semen analysis for males who have had abnormal semen analysis results at Visit 2 (Day 0) post-dose, Visit 3 (Day 14) or Visit 4 (Day 28) compared to baseline pre-dose Visit 2 results.

Corticosteroid usage will be documented and managed as necessary. Corticosteroid management can occur either during a scheduled visit, unscheduled visit, or phonecall follow-up based on the investigator's discretion.

Phone call follow-up (Approximately 2 and 4 months after Visit 8 (-Day 84)
The following assessments will be performed: completion of ABQOL questionnaire, adverse event assessment, and concomitant medication.
Corticosteroid usage will be documented and managed as necessary.

Study Duration

Study duration for each patient (following the screening period) will be up to approximately 204 days

Screening period: Up to 4 weeks

Treatment period: 28 days (\pm 2 days)

Follow-up period: 56 days (\pm 2 days) or 90 days (\pm 2 days) for males who have had abnormal semen analysis results post-dose Visit

_

 $^{^{}a,b}$ Study visits 3 through 9 have a ± 2 day window. The window is calculated from the actual visit day compared to baseline (Day 0), (e.g., for Visit 6 (Day 56) the window would be Day 54 to Day 58)

	2 (Day 0), Visit 3 (Day 14) or Visit 4 (Day 28) compared to pre-dose Visit 2 (Day 0) results; 2 and 4 months follow-up phone call after Visit 8 (Day 84).	
Number of Patients	Up to 15 patients are expected to be enrolled in this study. Recruitment will be competitive.	

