### 1 Introduction

### 1.1 General

Bertilimumab is the first monoclonal antibody to specifically neutralize human eotaxin-1 (eotaxin). Bertilimumab has been shown to inhibit eotaxin-stimulated migration of cells and may therefore be useful in the treatment of human diseases such as Bullous Pemphigoid (BP), where eosinophil accumulation is an important feature.

The purpose of this study is to provide proof of concept for the treatment of BP with bertilimumab. This study will provide both safety and efficacy data for internal decision-making regarding further development of bertilimumab in BP. Its efficacy in newly diagnosed patients would be proven by allowing reduced initial doses of corticosteroids and a reduced cumulative dose of corticosteroids by facilitating rapid tapering to 10 mg prednisone equivalent or lower after initial control of BP lesions. Its efficacy in patients resistant to corticosteroid tapering would be proven by allowing patients to be tapered down from corticosteroids without flaring and/or allowing smaller doses of oral corticosteroids to control the disease.

The study will investigate newly diagnosed adult patients and adult patients resistant to corticosteroid tapering with moderate to extensive BP. The treatment period will include three IV infusions of 10 mg/kg bertilimumab on study Days 0, 14 (±2 days) and 28 (±2 days) and a follow-up period up to Day 84 (or Day 118 for males who have had abnormal semen analysis results on Day 0, Day 14 or Day 28) relative to pre-dose Visit 2. Patients will receive concomitant oral steroids during the treatment and follow-up period.

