#### Handling of missing data:

Missing data will not be imputed, i.e. only observed data will be used.

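### Cumulative prednisone by visit has no rule for patients who withdraw; averaged over those still observed, it understates steroid use if patients who cannot taper leave

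*SAP*

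**What the plan says.** SAP 7.2.1 (Prednisone Dose), step 4, defines the quantity within a patient: "The cumulative prednisone dose (mg) for each period will be calculated as the sum of the total prednisone dose (mg) over all preceding periods", counted from Visit 2. Step 5 repeats this in mg/kg. Neither step names the patients over whom the result is averaged.

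Two other places bear on that:

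- SAP 6.2.2, on missing data: "Missing data will not be imputed, i.e. only observed data will be used".
- SAP 9.4.1, Prednisone dose: "Descriptive statistics of prednisone doses (mean dose, weight adjusted mean dose, cumulative dose and weight adjusted cumulative dose) will be presented by visit". Mean plots of both cumulative versions are also listed there.

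The SAP does not say whether a withdrawn patient's total is dropped, held or extended, and it plans no fixed-cohort or sensitivity summary. The success/failure rule in SAP 7.2.1 concerns only the 10 mg/day dichotomy at Visit 8. Under Protocol 4.5, patients who withdraw after dosing are not replaced.

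**The concern.** A patient's cumulative dose can only rise or stay level. A mean of cumulative doses over a shrinking group lacks that property: when a patient leaves, everything that patient has taken so far leaves the mean too. The later points then describe a different, smaller group. If the leavers are those who could not reduce their dose, the remaining mean looks better than the cohort's experience.

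The quantity matters to the plan's own argument. SAP 1.1 says that efficacy in newly diagnosed patients would be shown partly through "a reduced cumulative dose of corticosteroids by facilitating rapid tapering to 10 mg prednisone equivalent or lower", and SAP 7.2.1 places cumulative dose among the main efficacy endpoints. The sample is small ("Up to 15 patients are expected to be enrolled in this study") and there is no control arm, so two or three leavers can move the reported figure noticeably.

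**Working it through.** Neither document states an expected cumulative dose or a dropout rate, so there is no planned figure to reproduce. The check is an illustration by direct arithmetic.

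**Inputs from the documents**
- 15 patients (Protocol Synopsis, upper limit).
- Start at 30 mg/day (Protocol 6.8.1, the Day 0 figure for newly diagnosed patients coming from 30–40 mg/day).
- Recommended taper (Protocol 6.8.1, Table 1): 5 mg per week down to 10 mg/day, then 2.5 mg per week.
- Six 14-day periods from Day 0 to Day 84, ignoring the ±2-day windows. Results are indexed by the day on which a period ends.

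**Assumptions not in the documents**
- 3 of 15 patients stay at 30 mg/day and leave at Day 42; the other 12 follow Table 1.

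**Step 1. Per-patient totals**
- Taperer, by week: 30, 25, 20, 15, 10, 7.5, 5, 2.5, then 0 mg/day. Period totals are 7×(30+25) = 385, 7×(20+15) = 245, 7×(10+7.5) = 122.5, 7×(5+2.5) = 52.5, 0 and 0 mg.
- Patient held at 30 mg/day: 14×30 = 420 mg per period.

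**Step 2. Means under each reading (mg)**

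| Day | Taperer | Held at 30 | All 15 followed | Observed only | Zero after leaving |
|---|---|---|---|---|---|
| 14 | 385 | 420 | 392 | 392 | 392 |
| 28 | 630 | 840 | 672 | 672 | 672 |
| 42 | 752.5 | 1260 | 854 | 854 | 854 |
| 56 | 805 | 1680 | 980 | 805 | 896 |
| 70 | 805 | 2100 | 1064 | 805 | 896 |
| 84 | 805 | 2520 | 1148 | 805 | 896 |

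- Day 42: (12×752.5 + 3×1260)/15 = 854.
- Day 84, all followed: (12×805 + 3×2520)/15 = 1148.
- Day 84, observed only: 805; 805/1148 = 0.70, so 30% low. Between Day 42 and Day 56 this mean falls from 854 to 805.
- Day 84, accrued dose kept and 0 mg added: (12×805 + 3×1260)/15 = 896; 896/1148 = 0.78, so 22% low.

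**Step 3. How far this depends on the assumptions**
- Leavers held at 20, 30 or 40 mg/day; 1, 3 or 5 leavers; leaving at Day 14, 28, 42, 56 or 70: 45 combinations. The observed-only Day 84 mean is too low in all 45, from −7% (1 leaver at 20 mg/day: 805 against (14×805 + 1680)/15 = 863) to −51% (5 leavers at 40 mg/day: 805 against (10×805 + 5×3360)/15 = 1657). The zero-afterwards reading runs from −2% to −56%.
- The observed-only mean actually falls at the first visit after leaving in 24 of the 45. In the other 21 it still rises. For example, with one leaver at 30 mg/day at Day 42 it goes from 786 to 805.
- Low-dose leavers: with 3 held at 10 mg/day, 805 against (12×805 + 3×840)/15 = 812, or −1%. With 3 held at 5 mg/day, 805 against (12×805 + 3×420)/15 = 728, or +11%.

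**Step 4. Running sum of period-wise means**
- All 15 to Day 42: 854. Then add the mean period dose of the 12 still observed: 52.5, 0, 0. Total 906.5, about 907 mg.
- It cannot fall, but 906.5/1148 = 0.79, so 21% low. It closes 906.5 − 805 = 101.5 mg of the 1148 − 805 = 343 mg gap, about 30%.

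**The case against.** The strongest reply is that step 4 sets no denominator. A leaver does have preceding periods, and milligrams already recorded are observed data, so the SAP could be read as keeping them. On that reading the fall from 854 to 805 disappears. This stands as a point about wording, but it does not rescue the analysis: adding 0 mg after withdrawal also understates use (896 against 1148 mg).

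A reader might infer more than the documents support:

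- **That the planned table is biased toward steroid sparing whatever happens.** The direction depends on who leaves, and low-dose leavers reverse it under the observed-only reading. Failure to taper is not among the example reasons for discontinuation in Protocol 4.5. Protocol 6.8.2 lets rescued patients stay in, and the taper is only recommended. Protocol 4.5.1 allows local standard of care after non-response or flare, in the section on early discontinuation, but does not say that such patients must withdraw.
- **That the mean must fall or go flat.** It often still rises, only too slowly. Nor is flatness itself a sign of bias: a patient who follows Table 1 from 30 mg/day is at zero from Day 56, so that patient's true curve is flat from then on.

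Some transparency is already planned: the number of observations (SAP 9), dropouts with reasons (SAP 9.1) and corticosteroid records by subject (SAP 9.3.2). With at most 15 patients, a careful reader could trace the problem. None of these items corrects the mean. It is also fair that the study is descriptive, that safety is primary, and that cumulative dose is not among the endpoints in Protocol 2.2.

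**Conclusion.** The point holds in conditional form. Both available readings of the SAP understate cumulative prednisone if patients on higher doses leave before Day 84; the more natural reading can also produce a mean cumulative curve that falls. In the illustration the Day 84 figure is 30% or 22% low. Those percentages rest on an assumed number of leavers, leaving time and held dose, and on the premise that leavers would have stayed on that dose. They are not predictions. If nobody leaves before Day 84, the problem does not arise.

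The SAP should be changed, because a main efficacy display can mislead on a quantity that SAP 1.1 ties to proof of efficacy and the remedy uses data already collected. It does not affect the primary safety objective.

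**What to change.** In SAP 7.2.1 (steps 4 and 5) and 9.4.1, replace the visit-wise mean of cumulative dose, in mg and in mg/kg, along these lines:

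> For each period, the mean prednisone dose will be calculated among efficacy-population patients under observation in that period. The cumulative curve is the running sum of these means, shown with n at each visit. It assumes that leaving is unrelated to dose.

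That assumption is the doubtful one (907 against 1148 mg in the illustration), so the running sum should not stand alone. Add the Day 0–84 cumulative dose for every patient in the efficacy population, under two stated rules for time after withdrawal: last recorded daily dose continued to Day 84, and zero. In the illustration the range is 896 to 1148 mg. The missing-data paragraph in SAP 6.2.2 needs an exception for this range, since it goes beyond observed data.

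Cost: a few sentences in the SAP and slightly more programming on corticosteroid records already collected. The reported figure may be less favourable if patients who could not taper left.
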